Procedures:	
See Schedule of Events for full details of protocol required procedures and applicable visits (and timings). Subjects who have completed 52 weeks of treatment with study drug in the AURORA 1 study and have provided signed and dated informed consent will be entered into this study. Subjects meeting the required eligibility criteria will be registered in the interactive web response system for the AURORA 2 continuation study, using the same subject number assigned in the AURORA 1 study. Subjects will continue to receive either Orelvo or matching placebo as randomized in the AURORA 1 study. Study drug treatment in the continuation study will remain blinded. Dosing of Orelvo or matching placebo in AURORA 2 is detailed in the Treatment section above. All subjects will continue to receive background therapy of MMF and/or oral corticosteroids, if applicable, starting at the same dose as at the end of the AURORA 1 study. When clinically indicated, subjects are allowed to be completely titrated off of oral corticosteroids; the sites will contact the Medical Monitor if the dose of oral corticosteroids is to be increased.
 
All subjects will receive up to 24 additional months of treatment, i.e., maximum 36 months in total (12 months in AURORA 1 plus 24 months in AURORA 2). After 12 months treatment in the AURORA 2 Continuation Study (i.e., 24 months treatment in total), subjects with controlled UPCR (in the Investigator’s opinion), taking the 23.7 mg (3 capsules) BID dose will be permitted to reduce the dose of Orelvo to 15.8 mg (2 capsules) BID if considered appropriate and at the discretion of the Investigator and after consultation with the Medical Monitor.
 
Subjects who permanently discontinue treatment with study drug will be treated at the Investigator’s discretion, and where appropriate in accordance with current guidelines (e.g., American College of Rheumatology (ACR 2012)). Subjects will return for all remaining study visits and assessments unless they have withdrawn consent. Those subjects who have withdrawn consent to complete remaining visits will be advised to return for the End of Treatment/Early Termination Visit.
 
All subjects will have a safety follow-up visit after the last dose of study drug, and an assessment of vital status at 6 and 12 months post study.

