Sample Size:	
Subjects will enter this protocol from the AURORA 1 study in order to provide the opportunity of an additional 24 months of treatment (total of 36 months of treatment); no sample size calculation is required.

Statistical Methods:	
Analysis:
 
All statistical summaries and analyses will be undertaken at study closure once the last subject has completed the Visit 24 safety follow-up visit. A complete description of the statistical analyses to be performed will be presented in a Statistical Analysis Plan (SAP).
 
The study will incorporate an unblinded, interim analysis of both safety and efficacy data. The timing of this interim analysis is expected to be 3 months post the final subject final visit of the AURORA 1 study (i.e., when the last subject reaches Visit 16 of the AURORA 2 continuation study).

---

Populations:

The safety analysis set will consist of all subjects who receive at least 1 dose of study drug in the continuation study.

The efficacy analysis set will be based on the intent-to-treat (ITT) principles and will consist of all consented subjects.

Safety Endpoints:

The analysis and summary of the safety endpoints will be conducted on the safety set.

Adverse events will be aggregated by System Organ Class and preferred term and presented as summary tables.

Laboratory values (based on results from the central laboratory), vital signs and other safety parameters will be summarized by visit as absolute values and change from AURORA 1 baseline. Laboratory values outside of defined normal ranges will be summarized.

Efficacy Endpoints:

All the secondary efficacy analyses will be performed on the ITT set. Data for each visit (as well as change from AURORA 1 study baseline as required) will be summarized by treatment group and visit for each secondary endpoint.

The following key secondary efficacy endpoints will be analyzed using the ITT population using logistic regression with terms for treatment group, baseline UPCR, biopsy class and MMF use at baseline (from AURORA 1) in the model.

- Proportion of subjects in renal response at Months 12, 18, 24, 30, and 36.
- Proportion of subjects in partial renal response at Months 12, 18, 24, 30, and 36.

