### **6.2 Blinding**

Study drug treatment in the continuation study will remain blinded.

In order to preserve the double-blind design, subjects that consented to the placebo group will be matched to the active dosage groups. Dosing schedule in the placebo group will be the same as that of the active treatment group. To this end, the double-blind nature of this study preserves the blind with respect to active study treatment and placebo.

All study personnel and subjects will be blinded to the study treatment administered during the study. Orelvo and placebo will be identical in taste, smell, and appearance. The site staff, monitors, and study subjects will remain blinded until the end of the study. In case of emergency, the unblinding process below should be followed.

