## 10.2.2 Causal Relationship Categorization

An Investigator who is qualified in medicine must make the determination of relationship to the study treatment for each AE and SAE. The Investigator must decide whether, in his or her medical judgment, there is a reasonable possibility that the event may have been caused by the study treatment. If there is no valid reason for suggesting a relationship, then the AE/SAE must be classified as not related. Otherwise, if there is any valid reason, even if undetermined or untested, for suspecting a cause-and-effect relationship between the study treatment and the occurrence of the AE/SAE, then the AE/SAE will be considered related. For SAEs, the Investigator must provide a brief comment explaining the rationale of his/her assessment of causal relationship on the SAE reporting form.

The following additional guidance may be helpful:

Term	Relationship	Definition
Related	Yes	The temporal relationship of the clinical event to study drug administration indicates a causal relationship, and other drugs, therapeutic interventions or underlying conditions do not provide a sufficient explanation for the observed event.
Not related	No	The temporal relationship of the clinical event to study drug administration does not indicate a causal relationship, or other drugs, therapeutic interventions or underlying conditions provide a sufficient explanation for the observed event.

If the causal relationship between an AE/SAE and the study treatment is determined to be “related”, the event will be considered to be related to study treatment for the purposes of expedited regulatory reporting. In circumstances where the Investigator has not yet provided his/her assessment about the relationship, the event will be considered as “related” and qualify for expedited regulatory reporting.

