### **13.10 Interim Analyses**

The study will incorporate an unblinded, interim analysis of both safety and efficacy data. The timing of this interim analysis is expected to be 3 months post the final subject final visit of the AURORA 1 study (i.e., when the last subject reaches Visit 16 of the AURORA 2 continuation study).

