6.11.7 Other Secondary Endpoints

Not applicable.

QMD Ref: [REDACTED]	Effective: 12Aug2019	Governing QMD: [REDACTED]
Confidentiality Statement		
This document is the property of [REDACTED] and may not be duplicated, copied, altered or removed from company without prior approval from [REDACTED] or in compliance with [REDACTED].		
REF: [REDACTED]		Page 27 of 37

		Controlled Quality Management Document	
		Sponsor:	Aurinia Pharmaceuticals
		Protocol Number:	AUR-VCS-2016-02
STATISTICAL ANALYSIS PLAN. PHASE 2-3-4			

A treatment-related TEAE is defined as a TEAE that is assessed by the Investigator or Sponsor as being related to study drug. If a TEAE has a missing relationship to study drug it is assumed to be related to the study drug for analysis purposes.

A disease-related TEAE is defined as a TEAE that is assessed by the Investigator or Sponsor as being related to the disease under study. If a TEAE has a missing relationship to the disease under study it is assumed to be related to the disease under study for analysis purposes.

Missing severity assessments will be summarised as severe.

Adverse event tables will comprise tables summarizing AURORA 2 TEAEs as well as some tables summarizing all TEAEs from month 0 to month 36.

The following tables will be presented for AURORA 2 TEAEs:

- Summary table of overall incidence, the number of events, relative risk and 95% CI (voclosporin:placebo) including the following top line summaries:
 - Any AE
 - Any TEAE
 - Any Treatment-Related TEAE
 - Any Serious TEAE
 - Any Treatment-Related Serious TEAE
 - Any TEAE Leading to Voclosporin/Placebo Modification
 - Any TEAE Leading to Voclosporin/Placebo Discontinuation
 - Any TEAE Resulting to Death
 - Disease-Related TEAE
 - Disease-Related Serious TEAE
- TEAEs by System Organ Class and Preferred term
- TEAEs by System Organ Class, Preferred term and severity
- Treatment-Related TEAE by System Organ Class and Preferred Term
- Treatment-Related TEAE by System Organ Class, Preferred Term and Severity
- TEAE by System Organ Class and Preferred Term Leading to Dose Modification
- TEAE by System Organ Class and Preferred Term Leading to Voclosporin/Placebo Discontinuation
- TEAE by System Organ Class and Preferred Term Resulting in Death
- Disease-Related TEAE by System Organ Class and Preferred Term
- Serious TEAE by System Organ Class and Preferred Term

QMD Ref: [REDACTED]	Effective: 12Aug2019	Governing QMD: [REDACTED]
Confidentiality Statement		

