7 INTERIM ANALYSIS

The study will be ongoing during regulatory interaction and as such, regular reporting events will be required to ensure authorities are provided the most up to date information available.

These reporting events will incorporate both safety and efficacy analyses.

Timing of the interim analyses will range from 3 months post the final subject final visit of the AURORA 1 study (i.e., when the last subject reaches Month 15 of the AURORA 2 continuation study) up to 6 months prior to the end of AURORA 2 (i.e., when the last subject reaches Month 30 of the AURORA 2 continuation study).

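### The SAP lets a Sponsor opinion alone make a TEAE treatment-related, although the protocol gives that decision to the Investigator and the documents do not clearly keep sponsor reviewers blinded through the interims

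*Protocol*

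**What the plan says.** On causality, Protocol Section 10.2.2 reads: "An Investigator who is qualified in medicine must make the determination of relationship to the study treatment for each AE and SAE". In the protocol, a sponsor opinion on causality appears in the SUSAR definition (Section 10.1.4), which concerns reporting. Section 10.2.4 adds that an adverse event cannot be assessed as related both to the disease and to study treatment.

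The SAP's adverse event section (6.12.1 in its table of contents; in the text available it follows the 6.11.7 heading because pages between are missing) reads: "A treatment-related TEAE is defined as a TEAE that is assessed by the Investigator or Sponsor as being related to study drug". A parallel sentence defines disease-related TEAEs in the same way. SAP Section 9, which lists changes from the protocol, does not mention either rule.

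On interim looks, the protocol plans one analysis, in the Synopsis and again in Section 13.10: "The study will incorporate an unblinded, interim analysis of both safety and efficacy data". Its timing is given as follows: "The timing of this interim analysis is expected to be 3 months post the final subject final visit of the AURORA 1 study", that is, when the last subject reaches Visit 16. SAP Section 7 says that "regular reporting events will be required to ensure authorities are provided the most up to date information available", covering safety and efficacy, and sets a window: "Timing of the interim analyses will range from 3 months post the final subject final visit of the AURORA 1 study", up to the time when the last subject reaches Month 30. Section 9 does not list this extension either.

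On blinding, Protocol Section 6.2 first says that all study personnel and subjects are blinded, then names roles: "The site staff, monitors, and study subjects will remain blinded until the end of the study". The sponsor is not named. Subjects are registered in AURORA 2 "using the same subject number assigned in the AURORA 1 study" and stay on the treatment they had there (SAP Section 5).

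**The concern.** Relatedness is a judgement, and in a double-blind trial its value depends on being made without knowledge of arm. The protocol secures this by giving the decision to the Investigator, who stays blinded. The SAP adds a second route through the Sponsor, for whom the blind is not clearly secured, in a study that produces unblinded output while follow-up continues.

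Two sets of results use relatedness. The first is the top-line adverse event table, where any treatment-related TEAE and any treatment-related serious TEAE are rows reported with a relative risk and 95% CI, together with the treatment-related and disease-related breakdowns by system organ class. The second is renal response, a key secondary endpoint. The third eGFR branch in SAP Sections 3.2.1 and 6.11.1 accepts a subject with eGFR below 60 and a confirmed fall above 20% only if no disease-related or treatment-related eGFR event is present.

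Separately, the two-assessor rule allows an overlap between categories that the protocol forbids.

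**Working it through.** The plan gives no figure to reproduce. The check is mainly a comparison of texts, with a little arithmetic on timing and on how the rule behaves.

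**1. Who decides**

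| Point | Protocol | SAP |
|---|---|---|
| Treatment-related | Investigator (10.2.2) | Investigator or Sponsor (6.12.1) |
| Disease-related | Investigator (10.2.4) | Investigator or Sponsor (6.12.1) |
| Both at once | Not allowed (10.2.4) | Possible under 6.12.1 |
| Listed as a change | – | No (Section 9) |

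**2. What the rule does.** An event is related if the Investigator or the Sponsor calls it related. The Sponsor can add a related call but cannot remove one. Let n be the number of subjects in an arm with an Investigator-related TEAE, and a the number who enter the row only through a Sponsor call. The relative risk based on the Investigator alone is then multiplied by

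(1 + a_V/n_V) / (1 + a_P/n_P), where V is voclosporin and P is placebo.

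This factor is 1 when upgrades are proportionate in the two arms, so distortion needs upgrading that differs by arm.

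**3. Illustration.** SAP Section 6.1.2 gives 216 subjects. Assume an equal split, 216/2 = 108 per arm, and 25% with a related TEAE, 0.25 × 108 = 27 per arm, so RR = 1.00.
- 5 added in the voclosporin arm only: 32/27 = 1.19. In the placebo arm only: 27/32 = 0.84.
- 10 added in the voclosporin arm only: 37/27 = 1.37. In the placebo arm only: 27/37 = 0.73.
- 5 added in each arm: 32/32 = 1.00.

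Only the 216 comes from the documents.

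**4. How much follow-up comes after the first interim.** Month 12 + 3 = Month 15 (Visit 16), and Month 36 − 6 = Month 30, so the window is consistent with the visit schedule. At Month 15 the last subject has 36 − 15 = 21 of 24 AURORA 2 months left (87.5%). If entry was uniform over A months (A is assumed), the mean months remaining are the average of max(0, 21 − u) for u from 0 to A:
- A = 12: 21 − 6 = 15.0, or 15/24 = 62.5%.
- A = 18: 21 − 9 = 12.0, or 50%.
- A = 24: 21²/(2 × 24) = 9.19, or 38.3%.

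The number of interims is not stated. Assuming at most one per three-monthly visit from Month 15 to Month 30, it would be 2 to 6.

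**5. Renal response.** Take a subject with UPCR, rescue and steroid criteria met, eGFR below 60, a confirmed fall above 20%, and an eGFR event that the Investigator called unrelated to drug and to disease. On the Investigator's call the subject is a responder. If the Sponsor calls the event related, the subject becomes a non-responder. The criterion does not itself say whose call applies; this step carries the 6.12.1 definition over to it.

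**6. Overlap.** If the Investigator calls an event disease-related and the Sponsor calls it drug-related, 6.12.1 counts it in both sets of tables. SAP Section 6.2.16 makes an exception for this kind of conflict when the disease relationship is missing, so exclusivity seems to have been intended.

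**The case against.** The strongest reply is that the decisive link is absent. No section says that sponsor causality reviewers see arm data, that the interim gives them subject-level output, or when AURORA 1 codes are released. The reference in Protocol Section 6.2 to all study personnel may include them. Section 6.3 bars sharing emergency unblinding results with the project team, which shows intent. The unblinding manual, the DSMB charter and the DSMB SAP are separate documents, and the opening of SAP 6.12.1 is not in the text available, so a firewall may be described elsewhere. The SAP convention of sorting listings by treatment group and subject is general, and Section 7 mentions no listings. All of this stands: a reader might infer that the sponsor's reviewers will be unblinded, and the documents do not support that. What they show is that the point is left open.

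Nor does SAP Section 7 repeat the word unblinded; that comes from the protocol's single interim. Repeated unblinded interims are a reading of the two documents together, not a stated plan.

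It can also be said that Protocol Section 13.9 specifies no treatment-related table and leaves details to the SAP, so 6.12.1 fills a gap and need not appear in Section 9. The rule is also conservative, in line with counting missing relationships as related. This has some force for the listing in Section 9. It does not answer the inconsistency with Section 10.2.2, or the overlap barred by Section 10.2.4. In the renal-response criterion, an added related call can change an efficacy result.

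Finally, sponsor review carried out blinded would also close the bias risk. That is true, but the SAP does not require it, and it would not remove the overlap.

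**Conclusion.** The concern holds as an inconsistency in the stated rule, with a possible but unproven route to bias. The SAP widens who may classify an event as related, does not list this, and does so where sponsor blinding through the interims is not clearly stated.

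The reach is limited. A reader might infer that the primary endpoint is compromised. SAP Section 3.1 defines the primary adverse event estimand as the proportion of subjects reporting adverse events, with no causality condition, and the rows for any AE, any TEAE and any serious TEAE do not use relatedness. What is exposed is the treatment-related and disease-related rows and, if the 6.12.1 definition applies there, the third eGFR branch of renal response.

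The size is unknown. The relative risks of 1.19 and 1.37 rest on an assumed equal split, an assumed 25% rate and assumed one-sided upgrades; they show how the rule behaves and do not estimate the bias. The overlap between disease-related and treatment-related follows from the wording and needs no assumption about blinding. The missing statement of interim access and the unlisted extra interims are, on their own, points of clarification.

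**What to change.** In SAP Section 6.12.1, define treatment-related and disease-related TEAEs by the blinded Investigator's assessment alone, as in Protocol Section 10.2.2. State in Sections 3.2.1 and 6.11.1 that the renal-response eGFR criterion uses the same assessment. Show events upgraded by the Sponsor in a separate supportive table by arm. Leave expedited reporting, where either opinion may count, unchanged. With no sponsor additions in the analysed rows, the factor in step 2 is 1 by construction, and differing opinions can no longer put one event in both categories.

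Two clarifications should go with this. Protocol Section 13.10 and SAP Section 7 should say who sees interim output and at what level, including who holds subject-level AURORA 1 treatment codes until AURORA 2 lock. SAP Section 9 should list the move from one interim to several.

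The cost is some SAP wording and one extra table. The reported treatment-related count may be slightly lower, and the supportive table would show by how much.

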# SCHEMA

Notes: BID = Twice daily; IV = Intravenous; MMF = Mycophenolate mofetil.

## AUR-VCS-2016-02 SCHEDULE OF EVENTS

Visit 	Visit 15 (End of Treatment Visit of AURORA 1) 	Visit 16	Visit 17	Visit 18	Visit 19	Visit 20	Visit 21	Visit 22	Visit 23 End of Study/ Early Terminatio n 	Visit 24 Safety Follow-up 
Month 	12 ±10 days	15 ±10 days	18 ±10 days	21 ±10 days	24 ±10 days	27 ±10 days	30 ±10 days	33 ±10 days	36 ±10 days	37 ±10 days
Informed consent	✓									
Eligibility criteria	✓									
Physical examination 	(✓)								✓	
Vital signs (BP, pulse, temperature)	(✓)	✓	✓	✓	✓	✓	✓	✓	✓	✓
Kidney Biopsy 		✓								
ECG 	(✓)		✓		✓				✓	
Laboratory assessments 	(✓)	✓	✓	✓	✓	✓	✓	✓	✓	✓
Serum pregnancy test 	(✓)				✓				✓	

Visit 	Visit 15 (End of Treatment Visit of AURORA 1) 	Visit 16	Visit 17	Visit 18	Visit 19	Visit 20	Visit 21	Visit 22	Visit 23 End of Study/ Early Termination 	Visit 24 Safety Follow-up 
Month 	12 ±10 days	15 ±10 days	18 ±10 days	21 ±10 days	24 ±10 days	27 ±10 days	30 ±10 days	33 ±10 days	36 ±10 days	37 ±10 days
Urine pregnancy test 	✓	✓	✓	✓		✓	✓	✓		
AEs 	(✓)	✓	✓	✓	✓	✓	✓	✓	✓	✓
Concomitant medications 	(✓)	✓	✓	✓	✓	✓	✓	✓	✓	✓
Study treatment dispensing and compliance	✓	✓	✓	✓	✓	✓	✓	✓	✓ 	
MMF dispensing	✓	✓	✓	✓	✓	✓	✓	✓	✓	
Oral corticosteroids 	✓	✓	✓	✓	✓	✓	✓	✓		
Urinalysis	(✓)	✓	✓	✓	✓	✓	✓	✓	✓	✓
FMV urine collection	(✓)	✓	✓	✓	✓	✓	✓	✓	✓	✓

Visit 	Visit 15 (End of Treatment Visit of AURORA 1)	Visit 16	Visit 17	Visit 18	Visit 19	Visit 20	Visit 21	Visit 22	Visit 23 End of Study/ Early Termination	Visit 24 Safety Follow-up
Month	12 ±10 days	15 ±10 days	18 ±10 days	21 ±10 days	24 ±10 days	27 ±10 days	30 ±10 days	33 ±10 days	36 ±10 days	37 ±10 days
24-hour urine 	(✓)		✓		✓		✓		✓	
SELENA-SLEDAI	(✓)		✓		✓				✓	
Health-related QoL (SF-36) 	(✓)		✓		✓		✓		✓	
HRU 	(✓)	✓	✓	✓	✓	✓	✓	✓	✓	

- 
- 1 Month 12 Visit refers to the End of Treatment Visit 15 of the AURORA 1 (AUR-VCS-2016-01) study.
  - 2 Visit 15 assessments marked (-) will be provided from the results of the Week 52 Visit in the AURORA study.
  - 3 Subjects who discontinue therapy will attend their regularly scheduled study visits to the end of the study. Subjects who withdraw consent and terminate the study early should be advised to attend both Visit 23 and the Safety Follow-up Visit (Visit 24).
  - 4 Subjects will have a safety follow-up visit after the last dose of study drug, and an assessment of vital status at 6 and 12 months post study.
  - 5 Unscheduled visits/assessments can be done as needed. AEs, concomitant medications and verbal compliance check should be completed.
  - 6 Abbreviated physical examination only required. Height is not required.
  - 7 At sites that are able to meet the biopsy requirements, [REDACTED]
  - 8 During the study, in the event that a subject is noted to have a QTcF value exceeding 500 msec, or >60 msec more than baseline, the ECG will be repeated; see Section 9.1.4.1, [Procedures to Manage a Treatment-Emergent Increase in QTc](#).
  - 9 Laboratory assessments will be performed according to the schedule in Section 9.1.1, [Laboratory Assessments](#); subjects will be fasting for 8 hours on the day of study entry on Month 12 (Week 52/ End of Treatment Visit of the AURORA 1 study) and at Month 24 and Month 36 End of Study visit.
  - 10 Serum pregnancy test to be evaluated at central laboratory at Month 12 using AURORA 1 Visit 15 result, Month 24, and Month 36.
  - 11 Urine pregnancy test to be performed at Month 12 (AURORA 1 Visit 15) for subjects who consent for enrollment into the AURORA 2 continuation study. In addition, urine pregnancy tests to be performed at all other visits indicated (except Month 24 and Month 36 where serum pregnancy test is performed).
  - 12 AEs will be recorded after the subject signs the ICF.
  - 13 Concomitant medications include all herbal medicines and supplements taken by the subject.
  - 14 Compliance only.
  - 15 All subjects will continue to receive oral corticosteroids starting at the same dose as at the end of the AURORA 1 study. When clinically indicated, subjects are allowed to be completely titrated off of oral corticosteroids; the sites will contact the Medical Monitor if the dose of oral corticosteroids is to be increased.
  - 16 24-hour urine collection should begin 2 days prior to the scheduled study visit in order not to coincide with the FMV sampling due on the day of the study visit.
  - 17 For details on HRQoL assessments (SF-36), see Section 9.3.1, [Health-related Quality of Life Assessments \(HRQoL\)](#).
  - 18 For details on Healthcare Resource Utilization, see Section 9.3.2, [Healthcare Resource Utilization Assessment](#).

Abbreviations: AE=adverse event; BP=blood pressure; ECG=electrocardiogram; FMV=first morning void; HRU = healthcare resource utilization; ICF=informed consent form; LN=lupus nephritis; MMF=mycophenolate mofetil; QTcF=QT interval duration corrected for heart rate using method of Fridericia; SAE=serious adverse event; SELENA-SLEDAI=Safety of Estrogens in Lupus Erythematosus National Assessment - Systemic Lupus Erythematosus Disease Activity Index; SLE=systemic lupus erythematosus.

---

